8.1.1 Study Drug Accountability and Disposition

The Study Chair and site Principal Investigators are responsible for ensuring accountability for the investigational agent, including reconciliation of materials and maintenance of drug records.

Dispensing and administration of avelumab will be recorded following institutional practices. An accurate accounting will be available for verification. Accountability records will include:

• Confirmation of delivery to the site

- Inventory at the site
- Dispensing for each patient
- Return or alternative disposition of unused study drug

Upon completion or termination of the study, all unused and/or partially used avelumab will be destroyed at each site per institutional policy. It is the Principal Investigators' responsibility to arrange for disposal of all empty containers, provided that procedures for proper disposal have been established according to applicable federal, state, local and institutional guidelines and procedures, and provided that appropriate records of disposal are kept.

9.0 STATISTICAL CONSIDERATIONS

9.1 Study Populations

The Safety population will consist of all patients who have received at least one dose of Avelumab.

The Intention-to-Treat (ITT) population will consist of all patients who have enrolled to the study.

9.2 Sample Size and Primary Analysis

A Simon's optimal two-stage design will be used for this cohort. The primary endpoint is overall response (CR or PR) rate at 6 months based on RECIST. If the overall response rate is $\leq 15\%$, we will consider the treatment as not meeting the threshold of going further. We will test the null hypothesis H0: $p \leq 15\%$ against the alternative hypothesis H1: p > 15%, where p is the overall response rate after six months of study treatment. The two-stage design proposed below will have an 80% power to reject the null hypothesis and conclude that the true overall response rate is above 15\%, if the observed overall response rate is $\geq 30\%$, at 10% significance level. The study design is described in detail is as follows:

Stage 1: 19 subjects will be accrued; accrual will be held until the progression results for all the 19 subjects are known for the first six months. The trial will be terminated at Stage 1 if \leq 3 of the 19 subjects have any CR/PR by 6 months; otherwise it will continue to Stage 2.

Stage 2: 20 more patients will be accrued. We will reject the therapy if, among all the 39 (19+20) subjects, the number of patients who have an overall response is ≤ 8 ; if ≥ 9 patients have a defined response by RECIST, the treatment will be successful. It will be concluded that our study treatment is associated with an overall response in more than 15% of patients.

Early stopping probability: Under this design, if the null hypothesis is true, the probability of stopping the trial early will be 68.4%. The sample size calculation was done using PASS version 8.0.16 (released January 27, 2011).

Final efficacy analysis will calculate the UMVUE estimate, p-value and 95% CI for the response rates.³²⁻³³ The calculation will be performed using R *clinfun* package (www.r-project.org).

9.3 Accrual

A minimum of 6 patients with R/M NPC are evaluated monthly across all 7 institutions included in this study. We therefore anticipate this study would require no more than 12 months to accrue.

9.4 Secondary Efficacy Analyses

Secondary analysis will present duration of response, progression-free survival, and overall survival. We will estimate median survival times together with their 95% confidence intervals, and report number of events, as well as Kaplan Meier plots with 95% confidence bands.

9.5 Secondary Safety Analyses

Analyses will be performed for all patients having received at least one dose of study treatment. The proportion of subjects experiencing adverse events, serious adverse events, and treatment delays will be summarized. Tolerability will be assessed based on dosage delays and discontinuation due to adverse events.

All AEs will be listed, documenting the course, outcome, severity, and relationship to the study treatment. Incidence rates of AEs and the proportion of subjects prematurely withdrawn from the study due to AEs will be shown.

9.6 Analysis of Biomarkers

The Chi-Square (or Fisher's Exact test) will be used to assess the association of categorical clinical data with categorical biomarker data. Time-to-event clinical data (PFS, OS) will be correlated with biomarker data using Kaplan-Meier methodology and Cox regression models. Logistic regression models will also be used to predict binary clinical data with baseline biomarker data. Finally, graphical methods and descriptive statistics will be used to summarize the data as well.

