2.3 Endpoints

Primary Endpoint:

1. Overall response rate (defined as complete or partial response) at 6 months based on RECIST.

Secondary Endpoints:

- 1. Duration of response, defined as time from documentation of tumor response to disease progression
- 2. Progression-free survival, defined as the time start of Avelumab until disease progression or death
- 3. Overall survival, defined as the time from start of Avelumab to death from any cause

- 4. Toxicity (grade 3 or higher), as defined by CTCAE 4.03.
- 5. Exploratory correlatives:
 - Tissue (new biopsy required upon study entry prior to therapy; repeat biopsy at time of progression will be encouraged but optional):
 - PDL1 expression by immunohistochemistry (ABC technique [Vector labs], using rabbit mAb 1:200 [Cell Signaling])
 - Immunophenotyping by flow cytometry:
 - T cell subsets (CD4, CD8, FOXP3)
 - Macrophages (CD68)
 - Cytokeratin 5/6 (by immunohistochemistry)
 - Peripheral blood (comparison of baseline and 12 week post-treatment samples, unless otherwise denoted)
 - TCR and BCR sequencing
 - T cell subsets (CD3, CD4, CD8, CD25, FOXP3)
 - B cells (CD19, CD20)
 - Macrophage I/II and myeloid-derived suppressor cells (MDSC) (CD16, CD68, CD206)
 - Natural killer cell activity (CD56, CD16)
 - EBV DNA plasma levels (will be performed at baseline, every 12 weeks after treatment initiation and at end of treatment)
- 6. Clinical activity of Avelumab as defined by overall response rate will also be measured utilizing immune-related RECIST.

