A newly obtained tumor specimen will be obtained prior to study entry (unless it is not feasible or deemed unsafe for the patient, archival tissue is available, and study chair has granted an exception) for the purposes of measuring PD-L1 expression, T cell subsets etc. Patients will also provide blood samples at baseline and 12 weeks after treatment initiation for correlative studies, including PBMCs, T and B-cell subsets, frequency and clonality. Peripheral blood will be collected at baseline, and then every 12 weeks after treatment initiation as well as at end of treatment for serial measurement of EBV plasma DNA levels. Additionally, at time of disease progression, patients will be encouraged but not mandated to undergo a second biopsy for study purposes to permit further correlative studies.

An end of treatment visit for clinical evaluations and safety assessments will be performed approximately 28 days (\pm 7 days) after the last dose of study drug. Patients discontinuing study treatment will be followed every 3 months for disease and survival outcomes.

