5.3.4 Additional Blood Collection for Correlative Studies (±7 days)

- Collect blood sample to measure EBV DNA plasma levels every 3 cycles (ie. cycle 4, 7, 10 etc) and at end of treatment.
- Collect blood sample for additional correlative studies at 12 weeks after treatment initiation (ie. cycle 4).

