5.3.5 Imaging (every 12 weeks ±7 days after treatment initiation)

- MRI, CT (neck and chest; abdomen/pelvis when indicated) or PET/CT (CT must be diagnostic quality)
- For patients who are clinically stable, a repeat scan will be required 4 weeks (±7 days) after initial radiographic findings of disease progression as a confirmatory assessment.

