5.5.3 Specimen Analyses

Analyses will be performed at the direction of the study chair, [name].

Tumor specimens will be evaluated by immunohistochemistry (IHC) for such biomarkers as:

- PD-L1 expression
- T cell subsets (CD4, CD8, FOXP3)
- Macrophage (CD68)

• Cytokeratin 5/6

PBMCs will be analyzed by flow cytometry for the following immune cell markers:

- T cell subsets (CD3, CD4, CD8, CD25, FOXP3)
- B cells (CD 19, CD20)
- Macrophage I/II and myeloid-derived suppressor cells (MDSC) (CD16, CD68, CD206),
- Natural killer cell activity (CD56, CD16)

Buffy coat samples will be analyzed for T cell receptor (TCR) and B cell receptor (BCR) sequencing.

EBV DNA plasma levels will be evaluated in peripheral blood at baseline, then every 12 weeks after treatment initiation and at end of treatment.

Fresh frozen core biopsies (when available) will undergo whole exome sequencing for neoantigen discovery.

Additional biomarkers may be examined as new information arises.

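### Does Section 9.6 expose the PFS and OS biomarker analyses to guarantee-time bias by not limiting them to baseline values?

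*Combined protocol and SAP*

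**What the plan says.** Section 9.6 has two relevant sentences. On survival outcomes: "Time-to-event clinical data (PFS, OS) will be correlated with biomarker data using Kaplan-Meier methodology and Cox regression models". On binary outcomes: "Logistic regression models will also be used to predict binary clinical data with baseline biomarker data". Only the second specifies baseline values.

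EBV DNA is measured repeatedly. Section 5.5.3: "EBV DNA plasma levels will be evaluated in peripheral blood at baseline, then every 12 weeks after treatment initiation and at end of treatment". Section 5.3.4 ties the draws to cycles: "Collect blood sample to measure EBV DNA plasma levels every 3 cycles (ie. cycle 4, 7, 10 etc) and at end of treatment". Section 4.1 describes the purpose as serial measurement. For the other blood markers, Section 2.3 plans a comparison of baseline with week 12.

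PFS and OS both start at the first dose (Sections 2.3, 6.2.2 and 6.2.4). Scans follow the same 12-week rhythm as the EBV DNA draws (Section 5.3.5). Relating molecular markers to disease outcome is a secondary objective (Section 2.2), but Section 2.3 calls the markers exploratory correlatives.

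The protocol names no landmark and no time-dependent covariate. It also has no rule for patients without an on-treatment sample. Equally, it defines no EBV DNA clearance, no negativity threshold and no on-treatment group.

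**The concern.** Two adjacent sentences treat timing differently, which invites the reading that on-treatment values are allowed in the survival models. In its usual form, Kaplan-Meier compares groups fixed at time zero. Put together, these suggest curves from first dose split by a result that is known only weeks or months later.

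That would be guarantee-time bias. A patient must stay alive, under follow-up and usually on treatment to be sampled, and each further sample is another chance to be classed as cleared. Long PFS would then produce the favourable class, not the reverse. At stake would be a spurious report that EBV DNA clearance predicts PFS or OS, from 39 patients at most. The primary response test would not be touched.

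**Working it through.** Section 9.6 states no figure, so there is none to reproduce. The check is what the wording permits, and what the worst permitted reading would do.

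**1. Readings that fit the sentence**

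| Marker value used | Time zero | Sound? |
|---|---|---|
| Baseline value as a fixed group | First dose | Yes: known for each sampled patient at time zero |
| Week-12 value, patients sampled and event-free at week 12 | Week 12 | Yes |
| Serial value as a time-dependent covariate in Cox | First dose, value updated at each draw | Yes |
| Later value as a fixed group | First dose | No |

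Three of the four are valid, and the text does not select the fourth.

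**2. How the fourth reading goes wrong**

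Inputs from the protocol: draws every 12 weeks and at end of treatment; scans every 12 weeks. A patient progressing at the first scan has 2 on-study draws (week 12, end of treatment). One progressing at week 48 has 5 (weeks 12, 24, 36, 48, end of treatment).

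Assumptions, not in the protocol: a clearance probability p per test, and a carry-over r. Each later result repeats the previous one with probability r and is otherwise redrawn. Then

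P(ever cleared in k draws) = 1 − (1 − p) × [r + (1 − r)(1 − p)]^(k − 1).

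With p = 0.30:

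| r | 2 draws | 5 draws |
|---|---|---|
| 0 | 1 − 0.7 × 0.7 = 51% | 1 − 0.7 × 0.7⁴ = 83% |
| 0.5 | 1 − 0.7 × 0.85 = 41% | 1 − 0.7 × 0.85⁴ = 63% |
| 0.8 | 1 − 0.7 × 0.94 = 34% | 1 − 0.7 × 0.94⁴ = 45% |
| 1 | 30% | 30% |

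**3. Effect on the test**

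Null simulation of ever versus never cleared from first dose: 39 patients, no marker effect, 3,000 trials per setting. Assumed: median PFS 12 or 24 weeks, p of 30% or 50%, median post-progression survival 26 or 52 weeks, progression dated at scans, and a draw at the progression visit. Only patients with an on-study draw are counted. False-positive rate at nominal 5%:

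| r | PFS | OS |
|---|---|---|
| 0 | 35–60% | 11–42% |
| 0.5 | 18–35% | 6–23% |
| 0.8 | 8–14% | 6–9% |
| 0.9 | 6–8% | 5–7% |
| 1 | 5–6% | 5–6% |

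The week-12 landmark gave 5–7% (PFS) and 5–6% (OS). Time-dependent Cox gave 4–6% for both.

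**4. Sensitivity to the assumptions**

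- *Another model.* With a 20% or 40% chance of a first negative at each draw and unsampled patients kept as not negative, the rates were 49–90% for scan-dated events and 71–99.8% for continuously observed events. Landmark and time-dependent analyses stayed at about 3–8%.
- *Results that never change.* This does not remove the bias in general. With continuously observed events, and early failures without a sample coded as not negative, the median hazard ratio was 0.41–0.76 and the false-positive rate 6–61%. With scan-dated PFS, where everyone reaches the week-12 draw, the hazard ratio was 0.99–1.01. The cause is having to survive to be classified, not the value changing.
- *Stopping treatment before progression.* Draws end with treatment, while disease follow-up continues (Sections 4.9 and 5.4). Adding independent discontinuation with an assumed mean of 48 weeks cut the PFS rate from 18–34% to 8–11% at r = 0.5, and from 8–12% to 6–8% at r = 0.8.

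So the rate runs from nominal to almost certain, driven by clearance rate, carry-over, discontinuation and coding of unsampled patients. The protocol gives none of these.

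**The case for a change.** The best case for a change is that it is cheap. Section 9.6 already specifies baseline for logistic regression, so two or three sentences would extend this to PFS and OS. They would need no new samples or design change. With a small trial and a marker that can be cut many ways, fixing the timing before the data are seen guards against a misleading clearance result. Marker correlation is also a listed secondary objective.

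Much of this stands. The gap is in the text, the mechanism is correct, and the remedies hold the error rate near nominal.

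It still does not show an error in the plan. The faulty analysis has to be supplied by the reader: ever versus never cleared appears nowhere in the protocol. Section 5.5 sets an exploratory goal centred on markers of response, not on survival by later clearance.

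More detailed rules also carry costs. Under the assumed medians, a week-12 landmark keeps only about 19 to 28 of 39 patients for PFS. A time-dependent model that admits patients only at their first on-treatment draw would discard the baseline EBV DNA value and the PFS events found at the first scan.

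**Conclusion.** The concern does not call for a change. Section 9.6 leaves the timing of the marker values open in its survival sentence, but it commits to no biased analysis, and the standard ways of carrying it out are valid. A competent analyst would use baseline values from first dose, analyse week-12 values from a week-12 landmark, and enter serial EBV DNA as a time-dependent covariate that starts at the baseline value.

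The possible harm is confined to an exploratory result. The Simon two-stage response test, its stopping rule and its sample size do not use biomarkers.

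No single figure for the bias can be defended. For the one faulty grouping examined, false-positive rates ran from about 5% to 99.8% across the assumptions. When a patient's successive results were strongly alike (carry-over 0.8 to 0.9), PFS rates were 6–14%, or 6–8% at 0.8 once earlier discontinuation was allowed for.

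The conclusion rests on the markers staying exploratory and on no on-treatment group being fixed from first dose. If a report did show curves from first dose by later EBV DNA status, the criticism would apply to that analysis.

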10.0 STUDY MANAGEMENT

10.1 Conflict of Interest

Any investigator who has a conflict of interest with this study (patent ownership, royalties, or financial gain greater than the minimum allowable by their institution, etc.) must have the conflict reviewed according to UCSD conflict of interest policy.

10.2 Institutional Review Board (IRB) Approval and Consent

The IRB should approve the consent form and protocol prior to any study-related activities. It is expected that the IRB will have the proper representation and function in accordance with federally mandated regulations.

In obtaining and documenting informed consent, the investigator should comply with the applicable regulatory requirement(s), and should adhere to Good Clinical Practice (GCP) and to ethical principles that have their origin in the Declaration of Helsinki.

Before recruitment and enrollment onto this study, the patient will be given a full explanation of the study and will be given the opportunity to review the consent form. Each consent form must

include all the relevant elements currently required by the FDA Regulations and local or state regulations. Once this essential information has been provided to the patient and the investigator is assured that the patient understands the implications of participating in the study, the patient will be asked to give consent to participate in the study by signing an IRB-approved consent form.

Prior to a patient's participation in the trial, the written informed consent form should be signed and personally dated by the patient and by the person who conducted the informed consent discussion.

10.3 Required Documentation For Multi-site Studies

Before the study can be initiated at any site, the following documentation must be provided to the UCSD Moores Cancer Center Clinical Trials Office:

- A copy of the official IRB approval letter for the protocol and informed consent.
- A copy of the IRB-approved consent form
- CVs and medical licensure for the principal investigator and any associate investigators who will be involved in the study.
- Form FDA 1572 appropriately filled out and signed with appropriate documentation. (NOTE: this is required if UCSD holds the IND. Otherwise, the affiliate Investigator's signature on the protocol is sufficient to ensure compliance)
- CAP and CLIA Laboratory certification numbers and institution lab normal values.
- Executed clinical research contract.

10.4 Patient Registration

All patients must be registered with the UCSD Moores Cancer Center Clinical Trials Office before enrollment to the study. Prior to registration, eligibility criteria must be confirmed with the UCSD Study Coordinator. To register a patient, call (858)-xxx-xxx Monday through Friday, 8:00am-4:30pm Pacific Time. Study sites other than UCSD must fax informed consent documentation, completed eligibility checklist, and all source documentation for eligibility confirmation to the UCSD Clinical Trials Office ([contact]).

Patients will be given a unique sequential study number at the time of enrollment. UCSD will fax the outside study site for confirmation of patient registration, the patient's study number, and ability to start study treatment.

10.5 Subject Data Protection

In accordance with the Health Information Portability and Accountability Act (HIPAA), subjects who have provided written informed consent must also sign a subject authorization to release medical information to the study Sponsor and allow a regulatory authority, or Institutional Review Board access to subject's medical information relevant to the study.

10.6 Data and Safety Monitoring/Auditing

In addition to adverse event monitoring and clinical oversight by the Study Chair, site principal investigator and co-investigators, quality assurance of the study will be performed by the UCSD Moores Cancer Center Clinical Trials Office internal monitor. Monitoring intervals will be dependent upon risk-based assessments.

This study will also use the UCSD Moores Cancer Center Data Safety and Monitoring Board (DSMB) to provide oversight in the event that this treatment approach leads to unforeseen

toxicities. Data from this study will be reported annually and will include:

- 1) the protocol title, IRB protocol number, and the activation date of the study.
- 2) the number of patients enrolled to date.
- 3) the date and site of patients' enrollment.
- 4) a summary of all adverse events regardless of grade and attribution.
- 5) a response evaluation for evaluable patients when available.
- 6) a summary of any recent literature that may affect the ethics of the study.

10.7 Adherence to the Protocol

Except for an emergency situation in which proper care for the protection, safety, and well-being of the study patient requires alternative treatment, investigators are required to conduct their research according to the plans reviewed and approved by the IRB.

10.7.1 Emergency Modifications

Investigators may implement a deviation from, or a change of, the protocol to eliminate apparent immediate hazards/risks to trial subjects without prior IRB approval. Any such emergency modification implemented must be noted and reported to the IRB along the lines of a protocol deviation or violation, depending on the nature of the modification.

10.7.2 Protocol Violations

Any unplanned variance from an IRB approved protocol is considered a violation and must be reported to the IRB in a timely fashion. For the UCSD IRB:

A. Major violations must be reported to the IRB within 10 working days of awareness of the violation.

Major violations include:

- Instances that have harmed or increased the risk of harm to one or more research participants.
- Instances that have damaged the scientific integrity of the data collected for the study.
- Results from willful or knowing misconduct on the part of the investigator(s).
- Demonstrates serious or continuing noncompliance with federal regulations, State laws, or University policies.
- **B.** Minor violations may be reported to the IRB at the time of the continuing review. Minor violations have no substantive effect on the risks to participants or on the scientific integrity of the research plan or the value of the data collected.

10.8 Amendments to the Protocol

Should amendments to the protocol be required, the amendments will be originated and documented by the Study Chair. It should also be noted that when an amendment to the protocol substantially alters the study design or the potential risk to the patient, a revised consent form might be required.

The written amendment, and if required the amended consent form, must be sent to the IRBs at each site and submitted to the FDA by the Study Chair for approval prior to implementation.

10.9 Record Retention

Study documentation includes all Case Report Forms, data correction forms or queries, source documents, Sponsor-Investigator correspondence, monitoring logs/letters, and regulatory documents (e.g., protocol and amendments, IRB correspondence and approval, signed patient

consent forms).

Source documents include all recordings of observations or notations of clinical activities and all reports and records necessary for the evaluation and reconstruction of the clinical research study.

Government agency regulations and directives require that the study investigator must retain all study documentation pertaining to the conduct of a clinical trial. In the case of a study with a drug seeking regulatory approval and marketing, these documents shall be retained for at least two years after the last approval of marketing application in an International Conference on Harmonization (ICH) region. In all other cases, study documents should be kept on file until three years after the completion and final study report of this investigational study.

